⁹ Spine DXA at screening will *only* be performed in cases where this is required by regulatory agency via documented request, subsequently approved by the SPONSOR. Patients who had BMD at the lumbar spine performed at screening (Visit 1) do not need to perform this procedure at Randomization (Visit 2).
¹⁰ Spine/hip DXA at 6 months will *only* be performed in cases where this is required by regulatory agency via documented request, subsequently approved by the SPONSOR. As with all follow-up DXA measurements, results will be masked unless Excessive Bone Loss (EBL) criteria are met.
¹¹ Perform at Month 36 or end of study/early discontinuation if before Month 36.
¹² Given that this is an event-driven study for morphometric vertebral, hip, and non-vertebral fractures, actual study duration is unknown, but is estimated to be 5 years including a 1 year recruitment period.
¹³ For patients with visits past 48 months, Telephone visits will be conducted every three months (e.g., Months 51, 57) procedures same as Month 45; a clinic visit for safety parameters every 6 months (e.g., Months 54, 66) procedures same as Month 42; and complete visit annually (e.g., Month 60) procedures same as 48. See section 3.2.3.6.9.
¹⁴ Telephone contact at least 14 days after the last dose of blinded study therapy or study discontinuation/end of study, whichever occurs later to collect SAE information.
¹⁵ Complete PE performed at end of study visit.
¹⁶ Bone biopsy at Month 24 and/or Month 36.
¹⁷ Plasma for proteomics archive to be obtained in all patients at Randomization, Month 12, and end-of-study (may not be Month 36).
T=Telephone follow-up; Mo.=Month; IRB=Institutional Review Board; ERC=Ethics Review Committee; F/U=Follow-up; EBL=Excessive Bone Loss

0822_018-04_ProtCore APPROVED — 02-Mar-2012

Worldwide

Restricted Confidential – Limited Access

0822, Protocol 018-04 Issue Date: 02-Mar-2012

17

Product: MK-0822

7

Protocol/Amendment No.: 018-04

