3.2.3.9 Discontinuation/Withdrawal From Study Therapy

Patients who stop taking study drug prior to the end of the study and agree to continue evaluation and participation in the study must be followed off-drug for the duration of the trial. If a patient discontinues blinded study therapy and/or from study participation, all end of study procedures should be performed.

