3.3.1.2 Bone Densitometry

Bone mineral density (BMD) will be measured by dual-energy x-ray absorptiometry (DXA) at the hip (total, femoral neck, trochanter) and lumbar spine for all patients at screening and Randomization, respectively, as well as at yearly intervals until the end of the study. Total body and distal forearm BMD will be measured in a 10% random subset of patients at Randomization and at yearly intervals until the end of the study. End of study BMD will be assessed unless <6 months have elapsed since the time of the last annual BMD measurements. All BMD scans will be centrally evaluated. The BMD QA center will review all baseline scans and confirm patients meet the BMD entry criteria prior to Randomization. The screening Visit 1 hip scan will be used to determine eligibility. Bone densitometry results at the follow-up visits will be blinded to patients and investigators to the extent possible. However, Investigators will be alerted if a patient meets the excessive bone loss criteria (Section 3.4.1.1).

Note: Spine DXA at screening and spine/hip DXA at 6 months will *only* be performed in regions where this is required by regulatory agency via documented request, subsequently approved by the SPONSOR.

All measurements will utilize the same limb and at least 3 vertebrae for all time points (as described in the central vendor DXA manual).

Note: Left hip must be used at screening, unless the left hip is not evaluable. Subsequent hip scans must be performed on the same hip scanned at baseline.

The same machine should be used for a patient throughout the study. Details on DXA acquisition and Quality Assurance will be included in the central vendor DXA manual.

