Two height measurements will be taken and recorded on the eCRF. If the 2 measurements differ by 4 mm or more, a third and fourth measurement will be obtained and recorded on the eCRF. The mean of the last 2 measurements will be used as the estimate of stature.

Change from baseline in stature at each of the yearly timepoints will be secondary endpoints. The number (percentage) of patients with a stature loss of greater than 1 cm during the study will also be analyzed, as will the rate of stature loss.

Height measurements performed on non-calibrated stadiometers or otherwise not obtained according to protocol procedures will be excluded from the analyses. Details on the criteria for exclusion from analysis will be documented in a memo before unblinding the team for the final analysis.

Secondary Bone Mineral Density Endpoints

The percent change from baseline in BMD measurements at the lumbar spine, total hip, femoral neck, trochanter, and 1/3 distal forearm will also be secondary endpoints. BMD measurements will be performed at baseline and each of the yearly timepoints.

For the lumbar spine (posterior/anterior [PA] view) measurements, mean BMD values from at least three evaluable vertebrae (four when available) from L1 to L4 will be used. If a vertebra becomes fractured during the study or was fractured at baseline, BMD data for this vertebra will be excluded from all analyses.

For the hip BMD measurement, the side of the hip measured must be consistent throughout the entire study. If the hip side that is being measured becomes fractured during the study, then data of that hip side will be excluded from the time of the fracture onward.

All analyses of BMD efficacy endpoints will incorporate the longitudinal BMD correction factor as determined by a single quality control center.

Product: MK-0822

44

Protocol/Amendment No.: 018-04

BMD at the total body and 1/3 distal forearm will only be performed in a random 10% subset of the randomized patients, identified by the IVRS system

Biochemical Markers of Bone Resorption and Bone Formation

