In addition, the percentage of patients who experienced a stature loss of greater than 1 cm during the study will be tabulated. A logistic model will be used to compare the two treatment groups, including terms for treatment, geographic region and stratum. The model-based odds ratio, and 95% confidence interval, will be provided as an estimate of the treatment effect.

The rate of stature loss will also be examined, using a mixed model with fixed effects for treatment, geographic region, stratum, treatment-year interaction and random intercept and slope (year). The within patient serial correlation of the values over time will be modeled by an unstructured covariance matrix. The magnitude of the slopes (rate of stature loss) will be summarized from the model, as well as the difference between treatments (mean and 95% CI). More detail on this mixed model is in appendix 6.7.

Bone Mineral Density Endpoints

For each body site and timepoint, BMD will be summarized at baseline and follow-up, by the mean and standard error, together with the mean percent change from baseline and its 95% confidence interval.

The percent change from baseline in BMD endpoints at all during-treatment time points will be analyzed using a longitudinal model with fixed effects for treatment, stratum, geographic region, and treatment-by-time interaction¹. The within patient serial correlation of the values over time will be modeled by an unstructured covariance matrix. More detail on this longitudinal model is in appendix 6.7.

The treatment effect at each of the on-treatment time points will be assessed by evaluating the within- and between-treatment group Least-Squares means (LS mean) and the associated 95% confidence intervals. Treatment difference will be tested at each of the on-treatment time points and adjustment for multiple testing will be handled as discussed below.

Similar analyses will be performed in the subgroup of bisphosphonate-intolerant patients (defined as patients with a contraindication or history of intolerance to bisphosphonates, or those considered by their physician to be unsuitable for bisphosphonate treatment).

A graphical presentation of the LS mean (+/-SE) change from baseline over time will also be provided.

Biochemical Markers

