Month 24 to 36 (1,096)	822 to 1,186
Month 36 to 48 (1,461)	1,187 to 1,551
If the study continues beyond Year 4, additional time windows will be defined similarly. All scans within a time window will be used, not only those closest to the target day.	

Table 3

Relative Day Ranges for Efficacy Analyses
BMD and Height Endpoints

Time Point (Target Day)	Full-Analysis-Set Analysis
Baseline (1)	-90 to 7
Month 6 (183)	8 to 273 [†]
Month 12 (365)	274 to 548 [†]
Month 24 (731)	549 to 913 [†]
Month 36 (1,096)	914 to 1,278 [†]
Month 48 (1,461)	1,279 to 1,643 [†]
If the study continues beyond Year 4, additional time windows will be defined similarly. [†] Provided measurement was not more than 30 days after the last dose of treatment in the complete study. As a supportive analysis, an analysis including all data, also beyond 30 days after the last dose will also be performed.	

Product: MK-0822

28

Protocol/Amendment No.: 018-04

Table 4

Relative Day Ranges for Efficacy Analyses Biochemical
Markers of Bone Resorption and Formation and
Indices of Calcium and Mineral Homeostasis

Time Point (Target Day)	Per Protocol Analysis
Baseline (1)	-30 to 1
Month 3 (91)	49 to 133
Month 6 (183)	141 to 225
Month 9 (274)	232 to 316
Month 12 (365)	323 to 407
Month 18 (548)	506 to 590
Month 24 (731)	689 to 773
Month 30 (913)	871 to 955
Month 36 (1,096)	1,054 to 1,138
Month 42 (1,278)	1,236 to 1,320
Month 48 (1,461)	1,419 to 1,503
If the study continues beyond Year 4, additional time windows will be defined similarly. Markers and selected indices are measured at baseline, Month 6, 12, 24, 36, 48, serum calcium is measured on more timepoints.	

Table 5

Relative Day Ranges for Efficacy Analyses
Bone Biopsy Endpoints

Time Point (Target Day)	Full-Analysis-Set Analysis
End of Study or Month 36 (1,096)	≥518

Product: MK-0822

29

Protocol/Amendment No.: 018-04

Table 6

Relative Day Ranges for Efficacy Analyses
Health Resource Utilization and Meal Questionnaires

Time Point (Target Day)	Full-Analysis-Set Analysis	
	Health Resource Utilization Questionnaires	Meal Questionnaires [†]
Baseline (1)	-90 to 7	-90 to 1
Month 3 (91)	8 to 137	2 to 137 [‡]
Month 6 (183)	138 to 228	138 to 228 [‡]
Month 9 (274)	229 to 319	229 to 319 [‡]
Month 12 (365)	320 to 411	-
Month 15 (457)	412 to 502	-
Month 18 (548)	503 to 593	-
Month 21 (639)	594 to 685	-
Month 24 (731)	686 to 776	-
Month 27 (822)	777 to 867	-
Month 30 (913)	868 to 958	-
Month 33 (1,004)	959 to 1,050	-
Month 36 (1,096)	1,051 to 1,141	-

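### Month 6 BMD is a tested full-FAS time point, although Month 6 DXA is scheduled only where a regulator requires it and routine scans elsewhere come from women who discontinued

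*Protocol*

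**What the plan says.** **Schedule.** Section 3.5.3 states: "BMD measurements will be performed at baseline and each of the yearly timepoints". The flow chart footnote (Section 1.7) adds: "Spine/hip DXA at 6 months will *only* be performed in cases where this is required by regulatory agency via documented request". Section 3.3.1.2 uses regions rather than cases: "spine/hip DXA at 6 months will *only* be performed in regions where this is required by regulatory agency". Height is scheduled at Month 12 and annually.

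**Analysis.** Appendix 6.7 Table 3, whose column is headed as the full-analysis-set analysis, lists "Month 6 (183) 8 to 273" for BMD and height. Its footnote sets a condition: "Provided measurement was not more than 30 days after the last dose of treatment in the complete study". A supportive analysis drops that limit. The PROC MIXED code in Appendix 6.7 uses month as a class variable, with levels defined by these windows. Section 3.5.5.1 says "Treatment difference will be tested at each of the on-treatment time points" and plots LS means over time. Section 3.5.5.3 runs the BMD and height step-down from the last time point back to the earliest. Its 50% completeness rule decides only which time point counts as last.

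**Scans at discontinuation.** Section 3.2.3.9 says: "If a patient discontinues blinded study therapy and/or from study participation, all end of study procedures should be performed". Those procedures include DXA, but Section 3.2.3.6.10 and Table 3-8 waive it when the last scan is less than 6 months old.

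**The concern.** The schedule and the analysis disagree on whether Month 6 is a BMD time point. Nothing in the model, the tests, the step-down or the plots limits Month 6 to women who were due a scan then.

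In the required regions the Month 6 sample is set by design and the randomised comparison holds. Elsewhere, the routine way to have a scan in the window is to stop therapy or leave the study. There, being observed depends on an event after randomisation that may be related to treatment or response. The missing-at-random discussion in Appendix 6.7 deals with data lost through discontinuation, not data present because of it. The model adjusts for four broad regions with additive terms, which does not separate scheduled scans from discontinuation scans.

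At stake is a Month 6 treatment difference reported, tested and plotted as a full-FAS result on a mixture of two differently selected groups.

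**Working it through.** **1. The plan's own BMD figures.** Section 3.5.5.4 gives a detectable difference of 0.3% with 6,000 per group, and 1% with 1,200 patients in total (SD 4%, alpha 5%, power 99%; two-sided assumed).

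MDD = SD × (z₀.₉₇₅ + z₀.₉₉) × √(2/n)

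- n = 6,000: 4 × (1.960 + 2.326) × √(2/6,000) = 0.313%
- n = 600: 4 × (1.960 + 2.326) × √(2/600) = 0.990%

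Both reproduce. The 0.3% does not describe Month 6. Of 16,300 women, required regions holding 5%, 10% or 20% (assumed) would schedule 815, 1,630 or 3,260 scans. The same formula then gives 1.20%, 0.85% or 0.60%.

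**2. When a discontinuation scan is due.** With a Day 1 baseline scan, the 6-month waiver means no scan is due before about Day 183. Table 3 accepts a baseline from Day −90, so the earliest a scan is due for a woman with a usable baseline is about Day 183 − 90 = 93. The Month 6 window closes on Day 273.

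**3. How many women.** Section 3.5.5.4 Table 3-12 gives 13% drop-out over 2 years (non-vertebral rows) and assumes exponential drop-out.

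λ = −ln(0.87)/2 = 0.0696 per year

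- Days 183–273: exp(−λ·183/365.25) − exp(−λ·273/365.25) = 0.9657 − 0.9493 = 1.6%
- Days 93–273: 0.9824 − 0.9493 = 3.3%

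**4. Share of Month 6 scans.** Let p be the proportion of women in required regions and f the proportion from step 3. Assume every such discontinuer is scanned within 30 days of last dose.

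Share = f(1 − p) / [f(1 − p) + p]; coverage of the FAS = p + f(1 − p)

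| p (assumed) | share, f = 1.64% | share, f = 3.31% | coverage of FAS |
|---|---|---|---|
| 5% | 0.0156/0.0656 = 24% | 0.0315/0.0815 = 39% | 7–8% |
| 10% | 0.0148/0.1148 = 13% | 0.0298/0.1298 = 23% | 11–13% |
| 20% | 0.0131/0.2131 = 6% | 0.0265/0.2265 = 12% | 21–23% |

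**5. Sensitivity.** The hip rows of Table 3-12 give 20% over 3 years, so λ = −ln(0.8)/3 = 0.0744 and f = 1.75% to 3.5%. The shares become about 25–40%, 14–24% and 7–12%.

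**6. Height.** No height is scheduled at Month 6 in any region, so a Month 6 height would come essentially from women who discontinued.

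**The case against.** **The Month 6 window may only keep early scans out of Month 12.** On this reading Section 3.5.3 already fixes the BMD time points as yearly. That is plausible, but the model, test and plot text does not say so. Table 3 also lacks the note that Table 4 carries on which time points are actually measured. The conflict stands.

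**The longitudinal model handles incomplete data.** The unstructured covariance lets Month 6 estimates use later scans from women with no Month 6 scan, so coverage alone does not define the population described. This stands in part. Women who stop for good have few or no later values in the primary analysis, because of the 30-day limit, so their Month 6 values are not balanced by their own later data.

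**The consequence is small.** This stands. Month 6 is reached last in the step-down, after every later time point is significant.

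**Stronger readings a reader might infer.**
- *Many Month 6 scans come after only weeks of exposure.* Counting every drop-out to Day 273 gives 1 − exp(−0.0696 × 0.75) = 5.1%, and shares of 49%, 31% and 17%. That overlooks the 6-month waiver: a woman stopping at Week 4 is not due a scan.
- *Discontinuers pull the Month 6 effect down.* Required scans fall mostly at or after the Day 183 target, and Section 3.5.5.3 expects the BMD difference to grow with time. The effect could move either way.
- *The Month 6 to Month 12 slope is distorted.* No BMD slope is analysed; month is a class factor.
- *Only a few countries are involved.* The protocol gives no number.

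**Conclusion.** The conflict is real and worth correcting, but its reach is limited to Month 6. As written, the plan would formally test and plot a full-FAS Month 6 BMD effect that, outside the required regions, is routinely observed only in women who discontinued.

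Their share of Month 6 scans is about 24%, 13% or 6% (at most 39%, 23% or 12%) for required-region shares of 5%, 10% or 20%. These figures illustrate the scale and are not estimates. The regional shares are assumed, the drop-out rate is for leaving the study (treatment discontinuation may be higher), and not every discontinuer will be scanned within 30 days of last dose. Scans earlier than the waiver requires are not forbidden either. The documents do not support a direction of bias.

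Yearly BMD claims and the fracture endpoints are unaffected.

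**What to change.** In Section 3.5.5.1, Section 3.5.5.3 and Appendix 6.7:

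- State that the formal full-FAS BMD time points, for the model, tests, step-down and LS-mean plots, start at Month 12 and are yearly.
- Report Month 6 BMD descriptively by treatment, only for scheduled scans in the required regions, with a window around Day 183.
- Keep scans before Day 274 out of the Month 12 window, as Table 3 now does.
- Drop the Month 6 level for height.
- Add a note under Table 3 on which time points are measured, as Table 4 has.

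The cost is wording, plus a formal full-population Month 6 BMD claim that the schedule does not support. No yearly claim changes.

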3.5 DATA ANALYSIS

This section outlines the statistical analysis strategy and procedures. A stand-alone Statistical Analysis Plan (SAP), which details the statistical issues and methods for the study was issued prior to the unblinding of the data for the first interim analysis. The current protocol amendment (018-02) incorporates all details from the stand-alone SAP, according to current Merck guidelines. A separate SAP was created for the PK/PD analyses. The protocol may be further amended if changes are made to the primary or important secondary analyses in the course of the study. Changes to other analyses will be listed in the Clinical Study Report for the study, along with an explanation as to why they occurred and when they occurred.

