A similar FAS population will be used as the analysis approach for BMD endpoints and stature, including all randomized patients who took at least one dose of study medication and have the necessary on-treatment information. Missing data will be handled by the longitudinal model, therefore no imputation of missing data will be necessary. As indicated in appendix 6.7, BMD measurements taken more than 30 days after the last dose of study medication will primarily not be included in the analyses, for results to be consistent with those from phase IIb and future phase III studies. For consistency with the approach for fracture endpoints, a supportive analysis including these measurements taken long after the last dose will also be performed.

The analyses of biochemical markers of bone turnover and formation will be performed using the per-protocol approach. BMD at the total body and distal forearm and biochemical marker endpoints will only be performed for approximately 10% of the randomized patients.

Time to first major cardiovascular and cerebrovascular event will be handled similarly as clinical fractures and will be based on the FAS approach.

Summary tables for health resource and meal questionnaires and bone biopsies will be for the FAS population.

Safety analyses will be based on the "All-Patients-as-Treated" (APaT) population, which includes all randomized patients who received at least one dose of study medication. For safety analyses, patients will be included in the treatment group for the treatment they actually received. For safety analyses, missing data will not be imputed.

Product: MK-0822

47

Protocol/Amendment No.: 018-04

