Analysis of log-transformed fraction of baseline value in biochemical markers of bone resorption (s-CTX, u-NTx) and bone formation (s-BSAP, s-P1NP) will utilize the same longitudinal model as BMD endpoints. The means and the associated 95% CIs will be back-transformed for presentation and the delta method will be used to back-transform

¹ The protocol (018-00) foresaw a random intercept in the model. Due to the unstructured covariance matrix, the random intercept is redundant and therefore omitted from the model.

Product: MK-0822

50

Protocol/Amendment No.: 018-04

the between-treatment difference (in weighted LS means) and 95% confidence interval. Formal testing of treatment differences will only be performed for resorption markers. A graphical presentation of the weighted LS mean (+/-SE) change from baseline (after back-transformation) over time will also be provided, as well as a graphical presentation of the mean actual values over time by treatment. Formal testing of treatment differences will only be performed for resorption markers.

Indices of calcium and mineral homeostasis will be summarized in similar fashion to biochemical markers, and no statistical testing will be performed to compare the treatment groups.

In addition, frequency tables will be provided for the percentage of patients with 25-hydroxyvitamin D levels <9 , ≥ 9 to <20 , or ≥ 20 ng/mL at baseline and at Month 12.

Bone Biopsies

The 2-D Histomorphometry and 3-D μ -CT transilial bone biopsy measurements at Month 24 and 36 will be summarized (mean, standard error and 95% CI) for each of the treatment groups. The principle purpose of these analyses is to rule out an increased incidence of qualitative abnormalities (e.g. excessive osteoid, woven bone, mineralization defect, marrow fibrosis), the number (percent) of patients with a qualitative abnormality will therefore be summarized for both treatment groups, along with the Miettinen and Nurminen method [23] based 95% confidence interval on the difference in percentage. The incidence of qualitative abnormalities on the bone biopsies will be considered a safety endpoint rather than an efficacy endpoint.

Meal and Health Resource Utilization Questionnaires

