The “All Patients-as-Treated” (APaT) approach will be used, which includes all patients who were randomized to double-blind treatment and received at least one dose of study medication. For this analysis patients will be counted in the treatment group for the treatment they actually received: if patients received one dose of the medication they were randomized to, they will be considered in their randomization treatment group, only if they received none of their actual randomization treatment and received the other treatment they will be considered in the other treatment group.

For vital signs and laboratory safety endpoints the APaT approach will be used, including all patients who took at least one dose of double-blind study medication and had a baseline and on-treatment measurement. Missing data will not be imputed.

Clinical Safety

Summary statistics will be provided for the change from baseline at each on-treatment time point in weight, blood pressure and pulse rate, by treatment group. Height will be handled as an efficacy endpoint.

Laboratory Safety

The primary focus of laboratory data will be based, for each laboratory test, on the proportion of patients exceeding predefined limits of change from baseline and/or exceeding predefined values, at least once during treatment period, until 14 days after the last dose of double-blind treatment.

The predefined limits of change from baseline and predefined values are displayed in Table 1.

For those predefined limits characterizing a large increase from baseline and/or a large on-treatment value, a patient exceeding the predefined limit will be classified as “above limit.” For those predefined limits characterizing a large decrease from baseline and/or a low on-treatment value, a patient exceeding the **predefined limit will be classified** “below limit.” The proportion of patients exceeding the predefined limits will be presented for the treatment groups, together with the 95% confidence intervals on the difference between the treatments.

In addition to the analysis of predefined limits of change, the change from baseline at each of the on-treatment time points in laboratory tests will be summarized for each of the treatment groups. No tests will be performed on the laboratory data.

A listing of all laboratory tests performed is in the appendix.

Product: MK-0822

18

Protocol/Amendment No.: 018-04

Table 1

Predefined Limits of Change Definitions for Laboratory Tests

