Month 39 (1,187)	1,142 to 1,232	-
Month 42 (1,278)	1,233 to 1,324	-
Month 45 (1,370)	1,325 to 1,415	-
Month 48 (1,461)	1,416 to 1,506	-

If the study continues beyond Year 4, additional timewindows will be defined similarly.
[†] Meal questionnaire was only performed in the ~1,500 Lead Cohort patients.
[‡] Provided measurement was not more than 30 days after the last dose of treatment in the complete study.

Product: MK-0822

30

Protocol/Amendment No.: 018-04

Table 7

Relative Day Ranges for Safety Analyses
Clinical Safety and Laboratory Endpoints

Time Point (Target Day)	Blood Pressure, Heart Rate APaT Analysis	Weight APaT Analysis	Laboratory Tests APaT Analysis
Baseline (1)	-90 to 1	-60 to 1	-90 to 1
Month 3 (91)	2 to 137 [†]	2 to 137 [†]	2 to 137 [†]
Month 6 (183)	138 to 228 [†]	138 to 228 [†]	138 to 228 [†]
Month 9 (274)	229 to 319 [†]	229 to 319 [†]	229 to 319 [†]
Month 12 (365)	320 to 456 [†]	320 to 425 [†]	320 to 456 [†]
Month 18 (548)	457 to 639 [†]	488 to 608 [†]	457 to 639 [†]
Month 24 (731)	640 to 822 [†]	671 to 791 [†]	640 to 822 [†]
Month 30 (913)	823 to 1,004 [†]	853 to 973 [†]	823 to 1,004 [†]
Month 36 (1,096)	1,005 to 1,187 [†]	1,036 to 1,156 [†]	1005 to 1,187 [†]
Month 42 (1,278)	1,188 to 1,369 [†]	1,218 to 1,338 [†]	1,188 to 1,369 [†]
Month 48 (1,461)	1,370 to 1,552 [†]	1,401 to 1,521 [†]	1,370 to 1,552 [†]
APaT: All-Patients-as-Treated.			
[†] Provided measurement was not more than 14 days after the last dose of treatment in the complete study.			

For all endpoints, except morphometric vertebral fractures, in the event that a variable has more than one value in a day range, the value closest to the target day of the time window will be selected for the FAS analysis. If a patient has 2 values on this day, the mean of these 2 values will be taken for the analysis. For the per protocol approach, the measurement closest to the target day in the day range, which does not violate the protocol violation criteria will be selected.

For morphometric vertebral fractures, all available scans will be used to determine the presence of a fracture in a time window, not only the scan closest to the target day.

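### Table 5 gives bone biopsies a single window labelled Month 36 or end of study, so the planned Month 24 summary has no window and Month 24 specimens take the wrong label (minor)

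*Protocol*

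**What the plan says.** Section 3.5.5.1 of the protocol plans that "transilial bone biopsy measurements at Month 24 and 36 will be summarized" by treatment group, with mean, standard error and 95% interval. Section 3.5.3 likewise names Month 24, and Month 36 or end of study, as the time points for qualitative histomorphometry and for microarchitecture. About 200 biopsies are expected at each time point (3.2.3.6.8 and 3.3.1.7), and 3.3.1.7 lets a woman biopsied at Month 24 be biopsied again at Month 36.

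The windows are in Appendix 6.7. Table 5 has one biopsy row, "End of Study or Month 36 (1,096"), with day range 518 and above. On repeated values the appendix says that "in the event that a variable has more than one value in a day range, the value closest to the target day" is the one selected for the FAS analysis. The only endpoint exempted is this: "For morphometric vertebral fractures, all available scans will be used to determine the presence of a fracture in a time window". Section 3.5.4 ties biopsies to that population: "Summary tables for health resource and meal questionnaires and bone biopsies will be for the FAS population".

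On abnormalities, 3.5.5.1 says that "the number (percent) of patients with a qualitative abnormality will therefore be summarized for both treatment groups", with a 95% interval on the difference, and classes this as a safety endpoint. Section 3.5 says that the protocol "incorporates all details from the stand-alone SAP", so Table 5 is the operative text for the window.

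**The concern.** The text plans two biopsy time points and the window table defines one. Taken literally, Table 5 pools 24-month and 36-month specimens under a Month 36 or end-of-study label and leaves the Month 24 mean, standard error and interval with no rule for which specimens enter them.

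The selection rule adds a second effect. Where a woman has two specimens in the one window, only one is kept. The protocol gives ruling out an increased incidence of qualitative abnormalities as the principal purpose of these analyses, so it should be clear that no specimen drops out of that count by accident. Elsewhere the appendix writes such a rule where it wants one. Laboratory limits count if exceeded "at least once during treatment period, until 14 days after the last dose of double-blind treatment", and vertebral fractures use all scans. No equivalent sentence is written for biopsies.

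**Working it through.** **Inputs.** Month 24 target day 731 and Month 36 target day 1,096 (Appendix 6.7, Tables 3 and 5). Biopsy range: day 518 onward (Table 5). Visit window: plus or minus 3 weeks, or 21 days (Study Flow Chart), taken here to apply to the biopsy. About 200 biopsies at each time point (3.3.1.7). The number of women biopsied twice, r, is not given.

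**Which window a Month 24 biopsy falls in.** 731 − 21 = 710 and 731 + 21 = 752. All of days 710 to 752 are above 518, so every on-schedule Month 24 specimen falls in the only window and takes the Month 36 or end-of-study label. Month 36 specimens (days 1,075 to 1,117) fall in the same window.

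**Which value is kept when a woman has both.** Distance of the Month 24 specimen from target: 1,096 − 731 = 365 days (344 to 386 over the visit window). Distance of the Month 36 specimen: 0 to 21 days. The Month 36 value is kept and the Month 24 value leaves the window summary.

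**Could a Month 24 row have been lost from the table?** A separate Month 24 row would not cure the problem, because the Month 36 row would still start at day 518 and overlap any window around day 731.

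**Size.** Specimens in the window: 200 + 200 = 400. Women under the Month 36 label: 400 − r. Of these, biopsied at Month 24 only: 200 − r. Values dropped: r. The values of r below are assumptions spanning the possible range.

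| r (assumed) | Month 24 values dropped | Month 24 only, among women under the Month 36 label |
|---|---|---|
| 0 | 0 | 200/400 = 50% |
| 50 | 50 | 150/350 = 43% |
| 100 | 100 | 100/300 = 33% |
| 200 | 200 | 0/200 = 0% |

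At r = 0 nothing is dropped, and the mislabelling is at its largest.

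**Would the plan's own check show it?** Appendix 6.7 summarises the actual measurement day within each window to look for window bias, but only for morphometric vertebral fractures and BMD.

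**Check of the split.** The midpoint of the two targets is (731 + 1,096)/2 = 913.5, the same cut as Table 3 (549 to 913, then 914 to 1,278). With it, days 710 to 752 and days 1,075 to 1,117 fall in separate windows.

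**The case against.** The strongest reply concerns the abnormality count. A reader might infer that an abnormality seen only at Month 24 is lost from the safety comparison whenever the Month 36 specimen is normal. The documents do not establish that. Sections 3.5.5.1 and 3.5.5.2 count patients with an abnormality, and the ordinary reading of such a count includes a woman with any abnormal specimen. They also call it a safety endpoint, whereas Table 5 is headed as an efficacy window. On the other side, Table 3-10 lists the abnormality under the FAS, and Table 7, which holds the safety windows, has no biopsy row. The text supports both readings, so this is an ambiguity and not a demonstrated loss.

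Second, 3.3.1.7 sends details of biopsy procedure and analysis to a separate SOP, which is not at hand and may address the handling. That is a fair limit on the missing any-specimen rule. It does not remove the conflict between Table 5 and 3.5.5.1 within the protocol.

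Third, the low bound of day 518 may be meant to catch biopsies at an early end of study or discontinuation, since a flow chart note on the Month 36 visit allows for these. That is a plausible reason for the bound, but it still leaves Month 24 without a window.

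A reader might also suppose that a second biopsy long after Month 36 could displace the wrong value. The schedule does not support this: biopsies are set only at Months 24 and 36, and the end-of-study procedures in Table 3-8 include none.

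Finally, 3.3.1.7 sends the first 200 consenting women to Month 24 and later ones to Month 36, while 3.5.3 says that the time point is assigned at random. The contradiction is real, and one might infer a biased comparison from it. But treatment is randomised and no comparison of Month 24 with Month 36 is planned, so it is an editorial matter.

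**Conclusion.** The point holds, as a minor one. Table 5 is wrong as written: about 200 Month 24 specimens would be reported under a Month 36 or end-of-study label, less any dropped because the woman was biopsied again, and the Month 24 summary in 3.5.3 and 3.5.5.1 has no window. Under the FAS selection rule, each woman with two on-schedule biopsies loses her Month 24 value from the window summary. How many that is cannot be said from the protocol.

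Whether the same rule reaches the qualitative abnormality count is open on the text, subject to the SOP. The conclusion rests on biopsies being taken near their scheduled visits. The effect is confined to the secondary, exploratory and safety biopsy results. The treatment arms remain comparable and no primary fracture endpoint is touched.

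**What to change.** Split the Table 5 row into Month 24 (target day 731, day 518 to 913) and Month 36 or end of study (target day 1,096, day 914 onward). This accepts that an end-of-study or discontinuation biopsy before day 914 is grouped with Month 24 by its actual timing.

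Add one sentence: a patient counts as having a qualitative abnormality if any on-study biopsy shows one, and this count is exempt from the closest-to-target rule, as is already written for vertebral fractures.

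Two editorial corrections can go in at the same time. Replace the random-assignment sentence in 3.5.3 with the consent-order rule of 3.3.1.7, and align the time points in 3.5.5.2 (now Month 24 or end of study) with those in 3.5.5.1.

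The cost is one table row and three sentences, made before unblinding. It needs no extra procedures, patients or data.
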